## 10. ETHICAL CONSIDERATIONS

All ethical and regulatory practices should be adopted and practiced throughout the trial by all the concerned trial personnel, as outlined in the ICH-GCP guidelines and applicable regulatory requirements.

## 10.1. Ethics Committee review and communications

Study documents (protocol, PIS/ICF, etc...) will be submitted by the investigator to the respective ethics committee for its review and approval, after receipt of approval letter from ethics committee along with other local regulatory approval, the study will be initiated at the respective sites.

#### 10.2. Informed Consent Process

Informed Consent is documented by means of a written, signed and dated informed consent form.

According to ICH GCP guidelines 1.28 Informed consent process defined as "Process by which a subject voluntarily confirms his / her willingness to Participate in a particular trial, after having been informed of all aspects of the Trial that are relevant to the Subject's decision to participate".

## 10.2.1. LAR (Legally Acceptable Representative)

"An individual or juridical or other body authorized under applicable law to consent, on behalf of a prospective subject, to the subject's participation in the clinical trial.

#### 10.2.2. Impartial Witness

A person, who is independent of the trial, who cannot be unfairly influenced by people involved with the trial, who attends the informed consent process if the subject or the subject's legally acceptable representative cannot read, and who reads the informed consent form and any other written information supplied to the subject.

#### **10.2.3. Re-consenting Process**

Re-consenting may be required for various reasons including but not limited to cases where:

- When significant new information comes to light that affects the safety of the subjects and/or might have influenced the subject's original decision to take part.
- Protocol Amendments may require the ICF to be revised
   E.g. Changes in study procedures, entry criteria, patient numbers etc
   Sponsor decides whether the ICF needs to be modified

## 10.3. Subject Confidentiality

- Subject's identity will be maintained confidential and confidentiality of records and documents that could identify subjects will be protected, respecting the privacy and confidentiality rules in accordance with applicable regulatory requirements.
- Subjects must be identified only by their assigned identification number and initial on all CRFs and other records and documents submitted to sponsor.
- The investigator will keep a Patient Identification List with complete identification information (name, address, contact number etc...) on each subject.
- Documents not for submission to sponsor such as subject's written informed consent form should be maintained by the investigator in strict confidence.
- Monitors and auditors from sponsor, and representatives of IEC or other regulatory
  agencies will be granted direct access to subject medical records and other study
  documents for verification of study procedures and data without violating the
  confidentiality of the subject.
- The subject should be informed that by signing a written informed consent form, the subject or his/parent or guardian is authorizing such access.

#### 11. STUDY MONITORING

## 11.1. Monitoring Frequency and Agenda

Monitoring will be conducted based on the study phase, complexity and duration etc. and relevant information will be shared with the Investigators and staff regarding monitoring in advance. During each visit the monitor will discuss with the Investigator and Coordinator all relevant issues pertaining to the trial, validate the CRFs with the source data, identify and request for clarification in case of any discrepancies or errors. The Investigator / delegated site staff will provide source documents, completed CRFs, space and time for resolving the queries during the monitoring visit. The monitor will collect completed CRFs during each visit.

#### 11.2. Source Data Verification

The source data verification and review of records is necessary to minimize any errors in transcribing data onto the CRFs. The monitor will validate the CRF entries with the source data and subjects' records.

## 11.3. Data Clarification / Rectification

Data will be entered into the CRF by site personnel. Post data entry, source data verification will be completed by Study monitor / Clinical Research Associates (CRA). If any query requires clarification from site, data management personnel will raise the query. Based on query raised by data management personnel, site will respond to the query. If response for raised query is satisfactory, then data management personnel will close the query or if response for raised query is not satisfactory then data management personnel will re- query to site.

# 11.4. Close-out Meeting / Site Closure

At this visit, left over trial medication(s) and trial related materials will be collected. An accounting will be done of all materials supplied to the site, as well as all subjects screened and enrolled.

# 11.5. Trial Supplies Accounting & drug dispensing log

The trial medication dispensed /consumed must correspond with that sent to the site, as the use of this medication is restricted only for trial purposes. On completion of the trial, all remaining medication must be handed over to the sponsor.

## 11.6. Records Preservation and Archiving

The investigator & the sponsor will have to archive all documents related to the trial at their respective sites for a period of 05 years and /or as per the sponsor's decision. In the event of the investigator leaving the institution, the same must be handed over to his successor who will maintain custody of the documents. The information of the same should be sent to the sponsor.

# 11.7. Subject Screening Log

The trial site will maintain a record of all patients screened. This log will help to evaluate the total percentage of patients found eligible, from among those screened. Patient Enrolment and Visit Log

The trial site will maintain a log of all patients enrolled into the study in order that each patient entering into the study is accounted for. This is necessary to identify those subjects who are not on schedule for their scheduled visits and may need to be reminded to conform to follow up schedules.

# 11.8. Patient Identification Log

A log of patient identification will be maintained at the trial site. This is necessary to contact subjects to conform to follow up schedules or licensing authority auditing purposes.

#### 11.9. Informed Consent Forms

The informed consent is a process by which a subject voluntarily confirms his or her willingness to participate in a particular trial, after having been informed of all aspects of the trial relevant to the subject's decision to participate. The informed consent sheet will be provided in the regional language along with the English copy. Prior to screening each patient must give his consent for study participation in writing. The informed consent must be obtained in duplicate. One copy will be retained by the investigator & the other copy is to be given to the patient. If required, Audio-visual (AV) recording of entire process of subjects' Informed consent will be conducted in clinical trials, as per site specific or regulatory requirements.

#### 11.10. Source Documents

These comprise the patient's hospital case sheets; laboratory investigation reports, ECGs etc. These will be used to transcribe data onto the CRFs. These will have to be

DRL-IND-NDA03-ELO/2022

Dr.Reddy's

made available to the sponsor's representative at the time of monitoring in order to validate CRF entries.

#### 11.11. Study Documents

The sponsor will supply copies of protocol, patient informed consent form/patient informed assent form and patient information sheet [in English and relevant vernacular languages], diaries to the investigator. The sponsor will ensure that the translations and back- translations of the patient informed consent form/patient informed assent form and patient information sheet from English to the relevant vernacular languages is done in an appropriate manner and take certificate of translation from the translating agency.

#### 12. INVESTIGATIONAL PRODUCT MANAGEMENT

#### 12.1. Study Drugs

**Test drug:** Elobixibat 5 mg

**Comparator:** Placebo matching Elobixibat 5 mg tablet

The sponsor will supply the study drugs to the investigators duly labeled and packed. The sponsor will supply rescue medicine but not the concomitant medication.

**Method of assigning treatment**: Eligible subjects after confirmation of diagnosis and conformance with entry criteria will be randomized to any of the treatment groups. Study Medication will be dispensed to the randomized subjects.

**Storage conditions:** All study drug supplies will be stored as per COA or as per sponsor's / manufacturer's instructions. Until dispensed to the subjects, the study drug will be stored in a secure, temperature controlled, restricted access area accessible to authorized personnel only.

## 12.2. Packaging, Labeling and Storage

All study drug supplies will be labeled and must be stored in accordance with the sponsor's / manufacturer's instructions. Until dispensed to the subjects, the study drug will be stored in a securely locked area, accessible to authorized personnel only.

DRL-IND-NDA03-ELO/2022

## 12.3. Unused investigational products

The unused investigational products will be accounted for at all the sites at close out visit and must be handed over to the sponsor.

# 12.4. Blinding and Unblinding Procedures

Blinding is a procedure in which one or more parties to the trial are kept unaware of the treatment assignment(s). Single-blinding usually refers to the subject(s) being unaware, and double-blinding usually refers to the subject(s), investigator(s), monitor, and, in some cases, data analyst(s) being unaware of the treatment assignment(s).

#### 12.4.1. Randomization

The randomization codes will be generated by the Randomization Code Administrator, an individual within Statistical Programming who will generate the randomization codes and will not be assigned the role of Statistical Programmer for this study. The randomization codes will be provided in a secure manner.

# 12.4.2. Unblinding

Unblinding sealed envelopes will be provided to the site. In case the unblinding becomes mandatory, the investigator has to open the envelope carrying the randomization code of the subject and find out the study medication being given to the subject. Utmost care should be taken to ensure that the person unblinding the randomization code opens the correct envelope for the particular subject who requires unblinding.

If the blind is broken, the date, time, and reason must be recorded in the subject's source record, CRF, and any associated AE report. In case of accidental unblinding, the unblinding incident and unblinded subject must be listed as a major protocol deviation. Persons going for monitoring the study should ensure that unblinding (accidental / emergency) has not occurred at the site and blinding has been completely ensured. In case an unblinding has happened, the monitor should document the circumstances and reasons for unblinding.

.

## 12.4.2.1. Accidental Unblinding

In case of an accidental unblinding, the investigator shall promptly document and explain in detail to the sponsor the reasons for / situation that led to unblinding and inform the responsible Ethics committee. However, it is the responsibility of the investigator to ensure that accidental unblinding does not occur.

## 12.4.2.2. Unblinding for Regulatory and Analysis requirement at the end of study

For regulatory requirement, reporting of SAEs not previously unblinded at the site level, the blind will be broken for SAEs, in case of requirement.

The overall randomization code will be broken only when all final clinical data have been entered onto the database and all data queries have been resolved, and the assignment of subjects to the analysis sets has been completed.

# 12.5. Supplies Accountability

As the above is an investigational study, the trial medication is to be used for trial purposes only. For this reason, a log has to be maintained of all study medication received, consumed, left over. The remaining medication will be collected by the sponsor's representative at the time of trial closure. The remaining stationary will also be collected by the sponsor's representative at the time of trial closure and kept at the sponsor's place.

#### 13. STATISTICS and DATA ANALYSIS

#### 13.1. Study Subjects

Male and non-pregnant female subjects (18-65 years of age) with clinical diagnosis of chronic constipation will be included in the trial.

## 13.2. Sample Size Estimation

A total of 150 patients with chronic constipation will be enrolled in the study.

Assuming a significance level of 2.5% and a power of 95%, we require 60 completed subjects per treatment group (a total of 120 subjects in study) to prove superiority of Elobixibat.

Assuming ~20% drop-out rates, 150 subjects will be randomized in this study with 1:1 ratio (75 subjects per each arm) to Elobixibat 5mg vs Placebo.

## 13.3. Statistical Analysis

A Statistical Analysis Plan (SAP) will be prepared as a separate document and finalized before database lock. Any deviation from the original statistical plan will be described and justified in the final report, as appropriate. The procedure for accounting for missing, unused and spurious data will be included in the Statistical Analysis Plan. All statistical analysis will be conducted using SAS®, Version 9.4 or higher.

The accepted per-protocol (PP) population used for evaluation includes all randomized subjects who meet all inclusion/exclusion criteria, dosed a pre-specified proportion of the scheduled doses of the assigned product for the specified duration of the study, do not miss a pre-specified number of scheduled doses for more than pre-specified number of days, and complete the evaluation within the designated visit window with no protocol violations that would affect the treatment evaluation. The protocol should specify how compliance will be verified, (e.g., by the use of subject diaries).

The mITT and safety populations include all randomized subjects who use at least one dose of product.

Subjects who are discontinued early from the study due to lack of treatment effect should be included in the PP population. Subjects whose condition worsens and who require alternate or supplemental therapy, excluding pre-specified rescue therapies, for the treatment of constipation during the treatment phase of the study should be discontinued, included in the mITT and PP population analysis, and provided with effective treatment. Subjects discontinued early for other reasons should be excluded from the PP population but included in the mITT population. The protocol should clearly state how missing data will be handled in the statistical analyses and provide appropriate justification for the method chosen.

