#### 4. STUDY DESIGN & PLAN OF STUDY

## 4.1. Overview of the Study design

Study Type: Interventional

Study Design: Prospective, multicenter, randomized, double blind, parallel group, placebo controlled, phase III superiority study

Randomization: Subjects meeting the inclusion criteria and none of the exclusion criteria will be randomized to either of the 2 arms i.e. test arm or placebo arm.

The packaging of the test and placebo products will be similar in appearance to make differences in treatment less obvious to the subjects and to maintain adequate blinding of evaluators. Neither the subject nor the investigator will be able to identify the treatment. The containers will not be opened by the subject at the study center.

Method of Generating Random Sequence: Computer generated randomization.

Method of Concealment: Sequentially numbered, sealed, opaque envelopes.

Blinding/Masking: Double Blind

Dosing Schedule:

• Test Arm: Elobixibat tablet

The usual adult dosage is 10 mg of Elobixibat self-administered orally once daily before breakfast. The dose may be adjusted according to the patient's response, but the maximum daily dose is 15 mg. Therefore, Elobixibat tablet (10 mg oral once daily self-administered as two tablets of 5 mg) in patients with chronic constipation once daily for one week and then dose titration (up or down) will be done according to the patient's response.

• Comparator Arm: Placebo matching test product

Placebo tablet matching test product (10 mg oral once daily self-administered as two tablets of 5 mg) in patients with chronic constipation once daily for one week and then dose titration of placebo (up or down) will be done according to the patient's response.

Trial visits:

Visit 1# (Screening visit Day -28 to Day -15)

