#### 5.3. Withdrawal criteria

- A subject may be withdrawn from therapy
- On account of development of an intolerable adverse event.
- A female subject will be withdrawn if she gets pregnant during the course of the study.

- A subject may also be withdrawn based on the discretion of the investigator for any reason, if it is felt that his/her further continuation in the trial will adversely affect him/her, or, in the interests of the study.
- Subject will be considered to have withdrawn from the study if the subject is lost to follow-up, died, is no longer being followed at the investigator's discretion
- A subject may also be withdrawn if the subject volunteers to do so. The reason for discontinuation should be documented and all serious adverse events should be reported to the Medical Monitor from [name].

All the efficacy and safety parameters are to be assessed and all applicable activities of visit 4 will be conducted at the time of discontinuation of the study.

The primary reason for withdrawing from the study will be clearly documented in the subject's medical record and recorded on the CRF.

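### Section 13.3 points the evaluation of this superiority trial at the per-protocol set, gives mITT no rank, and lets per-protocol drop patients who stop for adverse events

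*Protocol*

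**What the plan says.** Section 4.1 describes the trial as "Prospective, multicenter, randomized, double blind, parallel group, placebo controlled, phase III superiority study".

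Section 13.3 then sets out the analysis populations:

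- **PP.** "The accepted per-protocol (PP) population used for evaluation includes all randomized subjects who meet all inclusion/exclusion criteria". Members must also meet dosing conditions and "complete the evaluation within the designated visit window with no protocol violations that would affect the treatment evaluation".
- **mITT.** "The mITT and safety populations include all randomized subjects who use at least one dose of product".
- **Stopping for lack of effect.** "Subjects who are discontinued early from the study due to lack of treatment effect should be included in the PP population".
- **Worsening that needs other therapy.** These patients are discontinued, "included in the mITT and PP population analysis, and provided with effective treatment".
- **Everyone else who stops early.** "Subjects discontinued early for other reasons should be excluded from the PP population but included in the mITT population".

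Section 5.3 lists reasons for withdrawal from therapy, among them "On account of development of an intolerable adverse event". Section 13.3 does not use the words adverse event in its population rules. The exclusion follows from reading its residual category together with Section 5.3.

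Section 13.3.1 describes the primary and secondary efficacy tests without naming an analysis set. Section 13.3.2, by contrast, does name the Safety Population for the safety analysis.

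**The concern.** In a superiority trial the comparison should rest on the patients as randomised. PP membership is decided after randomisation, by completion, by conduct and by the reason for stopping.

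The reason-for-stopping rule is uneven. Patients who stop for lack of effect, plausibly more often on placebo, stay in. Patients who stop for tolerability, plausibly more often on elobixibat, go out. The side-effect table in Section 1.2 lists abdominal pain (23.2%) and diarrhoea (14.4%) for the drug. Both concern the bowel, and the primary endpoint counts bowel movements, so the patients removed may differ in outcome from those who remain.

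If the superiority test were run on PP, the error rate and the estimate could both move away from their nominal values. Neither the direction nor the amount could be known in advance.

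**Working it through.** **1. Which set the protocol attaches to efficacy**

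| Place | What it assigns |
|---|---|
| 13.3, PP definition | described as the population used for evaluation |
| 13.3, mITT definition | membership only |
| 13.3, patients who worsen | enter both the mITT and the PP analysis; no ranking |
| 13.3.1, efficacy tests | no set named |
| 13.3.2, safety | Safety Population named |

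An mITT analysis is foreseen, but only PP carries a phrase that gives it an evaluative role.

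**2. Who leaves each set**

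| Reason for stopping early | PP | mITT (if dosed) |
|---|---|---|
| Lack of effect | kept | kept |
| Worsening, other therapy needed | kept | kept |
| Intolerable adverse event (5.3, within other reasons) | removed | kept |
| Other withdrawal | removed | kept |

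**3. The plan's own figure**

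Section 13.2 asks for 60 completers per arm and allows about 20% dropout: 60 / (1 − 0.20) = 75 per arm, and 2 × 75 = 150. This reproduces. The allowance lets 75 − 60 = 15 patients per arm leave the analysed set.

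**4. What the PP rule could do to the error rate (illustration)**

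From the protocol: 75 per arm, and two-sided tests at 0.05 (13.3.1), which is 2.5% in favour of the active arm.

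Assumed, because the protocol gives no values: the adverse-event stopping rate *p* in each arm, and the correlation ρ between staying on treatment and outcome.

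Model, with no treatment effect: outcome *y* ~ N(0,1) in both arms, and a latent score *l* = ρ*y* + √(1 − ρ²)·*e* with *e* ~ N(0,1). A patient stops for an adverse event if *l* falls below Φ⁻¹(*p*) and is then dropped from PP. Patients who stop for lack of effect stay in, as the rule says. A t-test is applied to those left. There were 20,000 simulated trials per scenario, so the Monte Carlo standard error at 2.5% is √(0.025 × 0.975 / 20,000) ≈ 0.1 percentage points.

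False wins for the active arm in PP:

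| Stops, active / placebo | ρ = 0 | ρ = 0.3 | ρ = 0.5 | ρ = −0.3 |
|---|---|---|---|---|
| 5% / 1% | 2.5% | 3.4% | 4.2% | 1.6% |
| 10% / 2% | 2.4% | 4.5% | 6.1% | 1.3% |
| 15% / 3% | 2.6% | 5.5% | 8.7% | 1.0% |
| 20% / 5% | 2.4% | 6.2% | 10.4% | 1.0% |

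Positive ρ means that patients who stop have worse outcomes; negative ρ means that they would have had better ones. With all 75 per arm analysed, the rate is 2.3-2.7% in every scenario.

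The 20% active rate would mean 0.20 × 75 = 15 patients, the whole dropout allowance, so that row is the upper end of what the plan provides for.

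**5. Limits of the illustration**

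It uses a continuous outcome and a t-test. Section 13.3.1 names a CMH test on responder proportions, so the table shows the mechanism and its possible scale, not the error rate of the planned test. The all-patients result also assumes a usable outcome for everyone. In the trial that depends on how data after withdrawal are handled.

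**The case against.** The strongest reply is that the sentence defines membership and does not choose the primary set. No sentence says that the superiority test is run on PP. Section 13.3 foresees analyses of both sets, and the sentence that removes other early leavers from PP keeps them in mITT. A separate SAP is promised before database lock, and ranking the sets is commonly left to it. As a supportive set, a PP population that drops early leavers and retains treatment failures is ordinary and harms nothing.

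Much of this stands. A reader might infer that the protocol has made PP its primary set and so broken the randomised comparison. The documents do not support that, because PP gets its role from a descriptive phrase and not from an assignment. Sizing on 60 completers does not prove it either; inflating for dropout is routine.

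A reader might also infer that adverse-event leavers will concentrate on elobixibat. Section 1.2 gives reaction incidences without a placebo column and without discontinuation rates, so *may* is the most that can be said. Nor can the bias be expressed as a share of the effect the trial is designed to detect, since Section 13.2 states no effect size, SD or responder rates.

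What does not stand is leaving the matter to the SAP. The point does not rest on silence: the protocol attaches an evaluative phrase to one set, and it is the wrong one for superiority. An SAP that made mITT primary would have to depart from that phrase. What Section 13.3 expressly passes to the SAP is the handling of missing, unused and spurious data.

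**Conclusion.** The point holds as a wording fault with consequences for the main test. The only efficacy pointer in Section 13.3 is to PP, mITT is unranked, Section 13.3.1 is silent, and the PP rule selects on the reason for stopping.

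If the tests followed that pointer, the one-directional error could lie anywhere from about 1% to about 10% against 2.5% under the assumed stopping rates (5-20% active, 1-5% placebo) and correlations (−0.3 to 0.5). It would stay near 2.5% if stopping were unrelated to outcome. Those rates and correlations are assumptions, and the documents fix neither the sign nor the size of the bias. The case for correction rests on the text and on the superiority objective, not on any one figure in that range. It should be corrected before the SAP is finalised.

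**What to change.** In Sections 13.3 and 13.3.1, name the mITT set as the primary set for every efficacy test: all randomised patients with at least one dose, analysed in the arm to which they were randomised, with data up to withdrawal. State that PP is supportive only, and delete the phrase *used for evaluation* from its definition.

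The cost is wording. The number randomised stays at 150. Sections 5.3 and 7.2 already call for Visit 4 procedures when a patient withdraws, so no new data collection is needed. The small downside is that the estimated effect may be less favourable than in PP.
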